**Table 4-1: Systemic Methylprednisolone equivalent dose conversion**

Medication	Route	Equivalent Dose (mg) [N2]	Methylprednisolone Equivalent Conversion Factor [N1]
Betamethasone	IV	0.19	5.26
Cortisone	PO	6.25	0.16
Dexamethasone	IV or PO	0.19	5.26
Hydrocortisone	IV or PO	5	0.2

Methylprednisolone	IV or PO	1	1
Prednisolone	PO	1.25	0.8
Prednisone	PO	1.25	0.8
Triamcinolone	IV	1	1

Source: <https://www.mdcalc.com/steroid-conversion-calculator>, consulted 25/Jan/2023

Notes:

- N1. Methylprednisolone equivalent conversion factor is calculated by dividing the equivalent dose for Methylprednisolone by the equivalent dose for each medication.
- N2. Systemic Methylprednisolone equivalent dose is calculated by multiplying the dose by the Methylprednisolone equivalent conversion factor.

#### 4.3.7 *Protocol deviations*

Protocol deviations will be identified and reported on the FAS by the process described in the current version of the Trial Protocol Deviation Plan. Protocol Deviations will be listed by subject for the PA based on the FAS.

Counts and percentages of subjects with clinical trial report (CTR) reportable protocol deviations by deviation category and overall will be summarized based on the FAS.

#### 4.3.8 *Primary Endpoints*

Safety analysis will be performed by Dose levels (Low Dose, High Dose, Total Randomized, Low Body Weight, Total), on the SAS.

##### 4.3.8.1 *Adverse events*

Adverse events (AEs) will be coded using Medical Dictionary for Regulatory Activities (MedDRA) version 24.0. The severity of all adverse events will be graded according to the National Cancer Institute (NCI) Common Terminology Criteria for Adverse Event (CTCAE) [NCI-CTCAE, 2017], version 5 (publication date: 27 November 2017). Adverse Events will be summarized descriptively by the frequency and incidence of subjects experiencing events corresponding to System Organ Class (SOC) MedDRA and Preferred Term (PT). Subjects with multiple occurrences of events will only be counted once at the maximum severity/grade to trial therapy for each PT, SOC, and overall. Summaries will be ordered by decreasing overall incidence in SOC; and by decreasing overall incidence of PTs within a SOC .

The overall observation period will be divided into mutually exclusive categories, including pre-treatment, on-treatment (treatment emergent), post-treatment:

- A treatment-emergent adverse event (TEAE) is defined as an adverse event with a start date and time on or after the first administration of apaglutide or having been present prior to the first dose of apaglutide but worsening in severity after starting treatment relative to the pre-treatment state. Adverse events are considered as TEAE until 28 days after the last dose of apaglutide received.
- A pre-treatment Adverse Event is defined as an AE occurring after the signature of the ICF and before the first dose.
- A post-treatment adverse event is defined as an AE occurring 28 days after the last dose.

Adverse events that are reported as possibly, probably, or definitely related to apaglutide therapy will be counted as related to trial therapy. Adverse events with a missing relationship will be considered as "related".

An overview of all Adverse Events will be provided.

All SAEs or AEs that led to withdrawal will be listed, Serious Adverse Events (SAEs) will be flagged within the listing.

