1.5 Trial Objectives, Endpoints, and Rationale

1.5.1 Trial Objectives

1.5.1.1 Primary Objective

- To assess safety and tolerability of apaglutide in subjects with SR lower GI-aGVHD Grade II to IV Mount Sinai aGVHD International Consortium (MAGIC) who are treated with SS and RUX

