2.2.2 Treatment, Optional Treatment, and Lower GI-aGVHD flare Treatment

Eligible subjects, weighing ≥ 50.0 kg, will be randomized to one of the two treatment arms (low dose or high dose in one of the three weight bands). The exact dose they receive at each visit will depend upon the weight band they fall into at baseline (in the range from 2.5 mg to 10 mg, see Table 4). Further details are provided in Section 4.2.1.1. Subjects who weigh 40.0– <50.0 kg will not be randomized but assigned to receive apaglutide 2.5 mg SC once weekly (LBW dose).

Subjects will receive their first dose of apaglutide concomitantly with RUX. In exceptional cases where concomitant administration is not possible, RUX should be administered at maximum 72 hours before apaglutide initiation.

Apaglutide will be administered via SC injection weekly for either 8 or 13 weeks. Subjects will be dosed weekly from Week 0 to Week 7 inclusive.

Apaglutide should be given at least until Week 8 unless the Investigator sees intolerable AEs that are clearly attributable to apaglutide. This will ensure that apaglutide is given enough time to fully establish its GI stabilization and regeneration effects. Should a worsening of a subject's GI-related symptoms occur shortly after starting apaglutide, adjustment of SS/RUX is the first recommended step.

If there is no complete lower GI-aGVHD response at Week 8, subjects will continue treatment from Week 8 to Week 12 inclusive. Treatment between Weeks 0 and 7 or between Weeks 8 and 12 should be continued even if a complete lower GI-aGVHD response is achieved. If the Investigator concludes that a subject is still benefitting from apaglutide treatment and a subject has no complete lower GI-aGVHD response at Week 13, apaglutide can be optionally continued for a maximum of 13 additional weeks (until Week 25, inclusive) or until a complete lower GI-aGVHD response is achieved, whichever comes first.

Lower GI-aGVHD flare treatment can start as per the protocol if a subject develops a lower GI-aGVHD flare between Weeks 9 and 25, and if treatment with apaglutide was previously stopped when lower GI-aGVHD CR was achieved at Day 56 (or when PR or CR was achieved at Day 91). The definition of a lower GI-aGVHD flare is given in Appendix 16.2.

Only one event of a lower GI-aGVHD flare can be treated with apaglutide until no later than Week 25. Apaglutide can be restarted at the same dose received at randomization.

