## 2 TRIAL OVERVIEW

### 2.1 Trial Design

This is a randomized, single-blind, proof of concept (POC) trial to evaluate the safety, tolerability, and preliminary efficacy of apaglutide in subjects with Grade II to IV (MAGIC, Harris et al., 2016) Steroid Refractory (SR) gastrointestinal (GI) acute graft versus host disease (aGVHD) on systemic steroids (SS) and Ruxolitinib (RUX), defined as best available therapy (BAT). The overall trial design (Figure 1) is described below similarly to the trial synopsis from the protocol:

- Screening/Baseline:

The screening process can start any time after clinical diagnosis of lower GI-aGVHD and SS initiation. The subject should sign the Informed Consent Form (ICF) before any other trial procedure. This period will last at maximum 12 weeks (Days -84 to Day -1).

Subjects will be randomized (Day 0/Week 0) and receive the first dose of apaglutide only if they developed SR lower GI-aGVHD and have started treatment with RUX (at most 72 hours before starting apaglutide). Thirty subjects, weighing  $\geq 50.0$  kg, will be randomized to two treatment arms (high dose or low dose of apaglutide) based on their body weight at baseline (three body weight ranges:  $50.0 < 60.0$  kg,  $\leq 60.0 < 80.0$  kg and  $> 80.0$  kg). In addition to the 30 subjects, a separate, non-randomized cohort of up to four subjects with body weights within the range  $40.0 - < 50.0$  kg will be assigned to receive 2.5 mg of apaglutide.

- Main Treatment:

Up to 34 subjects will receive apaglutide on a background of RUX and SS. Apaglutide will be administered subcutaneously once weekly for 8 weeks (Week 0 to Week 7, inclusive).

- Treatment extension:

Treatment will continue up to 13 weeks (Week 8 to Week 12, inclusive) if no complete lower GI-aGVHD response is achieved at Week 8.

- Optional Treatment:

Optional treatment for additional 13 weeks (Week 13 to Week 25, inclusive) is allowed if no complete lower GI-aGVHD response is achieved at Week 13. Optional treatment can only be started if additional apaglutide treatment would benefit the subject based on the Investigator's judgement.

- Lower GI-aGVHD flare treatment:

Lower GI-aGVHD flare treatment can start if a subject develops a lower GI-aGVHD flare between Week 9 and Week 25. Only one event of lower GI-aGVHD flare can be treated with apraglutide until no later than Week 25.

- Follow-up:

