#### *4.3.8.1.2 Treatment Emergent Adverse Events Analysis*

The following type of events will be summarized by SOC and PT:

- 1) Adverse Events
- 2) Serious Adverse Events (SAE)
- 3) Grade 3-5 AE

- 4) Grade 5 AE
- 5) AE leading to treatment discontinuation
- 6) AE leading to study discontinuation
- 7) AE leading to dose reduction
- 8) AE leading to dose interruption
- 9) Related AE
- 10) Related Grade 3-5 AE
- 11) Related Grade 5 AE

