**Footnotes to Table B1:**

1. The screening process can start any time after clinical diagnosis of lower GI-aGVHD and SS initiation; obtaining informed consent should be done before any other trial procedure:
  - a. If needed, screening can be performed on the same day as baseline, as long as all assessments required at screening and baseline are performed and the results are available **prior to randomization**
  - b. If the same assessment is foreseen at screening and baseline, and screening and randomization occur on the same day, then the assessment does not need to be repeated
2. Treatment should be continued until Week 7 inclusive, even if a complete lower GI-aGVHD response is achieved before Week 7 inclusive
3. If a lower GI-aGVHD CR is not achieved at Week 8, treatment should be continued until Week 12 inclusive; even if a CR is achieved before Week 12
4. Optional treatment can start if there is no complete lower GI-aGVHD response at Week 13 and if the Investigator considers that the subject could benefit from the additional apraglutide treatment. Treatment can continue for a maximum 13 weeks (until Week 25, inclusive) or until a complete lower GI-aGVHD response is achieved, whichever comes first
5. In case of lower GI-aGVHD flare, treatment can be re-started at the same dose given at randomization/Day 0 (e.g., if flare occurs at Week 17, treatment will be performed during visits at Weeks 17–25 or until a CR is achieved, whichever comes first). Treatment can continue for a maximum of 13 weeks (until Week 25, inclusive) or until a complete lower GI-aGVHD response is achieved, whichever comes first
6. All visit procedures are recommended to be done on the same day, unless specified otherwise
7. Ruxolitinib treatment should be initiated concomitantly with apraglutide (in exceptional cases where concomitant administration is not possible, RUX should be administered at maximum 72 hours before apraglutide initiation)
8. Randomization will be performed via IRT with subjects assigned to receive a low dose or high dose of apraglutide based on the weight band they fall into at baseline. Subjects below 50.0 kg will not be randomized but assigned into an open-label treatment group and will receive apraglutide 2.5 mg

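### Crude TEAE, AESI and AEPI percentages by dose mix tolerability with response-driven length of exposure, in a direction that cannot be known in advance

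*SAP*

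**What the plan says.** Safety is the primary objective (Protocol 1.5.1.1: "To assess safety and tolerability of" apraglutide), and the effect of the two dose ranges on safety is a secondary objective (Protocol 1.5.1.2).

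The window for a treatment-emergent event has no fixed end: "Adverse events are considered as TEAE until 28 days after the last dose of" apraglutide (SAP 4.3.8.1). The last dose depends on the course of the disease:

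- **Main treatment:** "Treatment should be continued until Week 7 inclusive, even if a complete lower GI-aGVHD response is achieved before Week 7 inclusive" (SAP Table B1, footnote 2).
- **Extension:** "If a lower GI-aGVHD CR is not achieved at Week 8, treatment should be continued until Week 12 inclusive" (footnote 3).
- **From Week 13 on:** "Optional treatment for additional 13 weeks (Week 13 to Week 25, inclusive) is allowed if no complete lower GI-aGVHD response is achieved at Week 13" (SAP 2.1). Protocol 2.2.2 adds a condition, "If the Investigator concludes that a subject is still benefitting from" the drug, and dosing ends once CR is reached.
- **Flare re-treatment:** one course, ending no later than Week 25, for subjects whose dosing had stopped after a response (Protocol 2.2.2).
- **Toxicity:** permanent stops under Protocol 2.2.6 and Table 6.

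For the TEAE tables, "The following type of events will be summarized by SOC and PT" (SAP 4.3.8.1.2). Each subject counts once per term (SAP 4.3.8.1), the denominator is the analysis set (SAP 4.1), and the low and high doses are shown together (SAP 4.3.8). AESI and AEPI tables are specified for treatment-emergent events only (SAP 4.3.8.2, 4.3.8.3). Infections and sepsis have a table to Day 91 (SAP 4.3.9.17). No other adverse event table uses a common window, and none is adjusted for exposure.

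**The concern.** A percentage of subjects with at least one event rises with the time over which events are counted. Here that time is partly an outcome of treatment. If the doses differ in CR rate, early stopping, flares or toxicity stops, their TEAE columns cover different lengths of follow-up, and a difference in percentages is not by itself a difference in tolerability. A real difference could also be masked.

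The same event can be classified differently. An event on Day 100 is treatment-emergent in a subject dosed to Week 12. It is post-treatment in a Week 8 complete responder who was not re-treated. In the second subject it still appears in the general post-treatment tables (SAP 4.3.8.1.3), but it drops out of the AESI and AEPI tables.

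**Working it through.** The adverse event sections state no figure to reproduce, so the check starts from the dosing schedule.

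**1. Windows (last dose day + 28).** Weeks convert to days as in Table B1.

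| Path | Last dose | Window closes |
|---|---|---|
| CR at Week 8, no re-treatment | Week 7, Day 49 | 49 + 28 = Day 77 |
| No CR at Week 8 | Week 12, Day 84 | 84 + 28 = Day 112 |
| Optional treatment, shortest | Week 13, Day 91 | 91 + 28 = Day 119 |
| Optional treatment, longest | Week 25, Day 175 | 175 + 28 = Day 203 |

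Flare re-treatment can also move the last dose to Week 25, so a Week 8 complete responder can reach Day 203. The longest window is 203/77 = 2.6 times the shortest. Protocol 2.2.6 stops can make a window shorter than 77 days.

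**2. Effect on a crude percentage.** Assume the same constant risk of 10% per 28 days on both doses. Then P(event by day d) = 1 − 0.9^(d/28):

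- Day 77: 25.2%
- Day 112: 34.4%
- Day 203: 53.4%

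Assume Week 8 CR of 60% on one dose and 30% on the other, with half of the subjects without CR taking optional treatment to Week 25. Their average risk is (34.4 + 53.4)/2 = 43.9%.

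- CR 60%: 0.6 × 25.2 + 0.4 × 43.9 = 32.7%
- CR 30%: 0.3 × 25.2 + 0.7 × 43.9 = 38.3%

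The gap is 5.6 points with no true dose effect. If optional treatment ends on average midway, at a window of (119 + 203)/2 = 161 days, the gap is 4.4 points. With optional uptake of 25% to 75% and windows to Day 203, it is 4 to 7 points. At 20% risk per 28 days and half uptake it is 62.5% versus 55.4%. A fixed Day 77 window gives 25.2% on both doses.

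**3. Is the direction fixed?** A simulation kept the risk identical on both doses (30% by Day 77) with Week 8 CR of 60% versus 30%. Among the remaining subjects, 30% reached CR by Week 13 and half of the others had optional treatment to Week 25. A varying share of subjects without CR at Week 8 died or stopped early: their last dose fell evenly over Weeks 0 to 7 and their window closed 1 to 28 days later. In the flare row, 20% of Week 8 complete responders were re-treated, with the last dose falling evenly over Weeks 12 to 25. Entries are the lower-CR dose minus the higher-CR dose, in percentage points.

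| Early death or stop among subjects without CR | 0% | 20% | 40% | 60% | 80% |
|---|---|---|---|---|---|
| Constant hazard, no flare | +5.3 | +3.5 | +1.5 | −0.4 | −2.1 |
| Constant hazard, 20% flare re-treatment | +4.2 | +2.3 | +0.1 | −1.3 | −3.5 |
| Hazard halving every 28 days, no flare | +0.9 | +0.4 | −0.5 | −1.1 | −1.8 |

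The sign depends on quantities that the documents do not give.

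**4. Size in subjects.** With 15 per dose (Protocol 7.4), 5.6 points is 0.056 × 15 = 0.84 of a subject. The standard error of a difference near 35% is √(2 × 0.35 × 0.65/15) = 17 points.

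**The case against.** The strongest reply is that no planned inference is harmed. Adverse events are summarised descriptively, SAP section 6 (item 12) drops the dose-effect endpoint because the doses will not be formally compared, and the illustrative gap is under one subject per arm. This stands, and it limits the weight of the point. It does not remove it: the columns remain side by side for the primary objective and will be read as a comparison.

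Second, the SAP gives context. Treatment duration and injection counts are tabulated by dose (SAP 4.3.6.1), post-treatment events have their own tables, and infections and sepsis have a Day 91 table. Unequal exposure will therefore be visible. It will not be linked to the event percentages, and the post-treatment tables do not complete the AESI and AEPI tables. Protocol 7.6.1 provides for event rates only if most subjects have repeated events of one type, does not say that they are exposure-adjusted, and is not carried into the SAP.

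Third, the Primary Analysis cuts the data when all subjects have reached Day 91 or withdrawn (SAP 1), so late enrollees cannot contribute the longer windows there. This narrows the contrast in that analysis. It also adds enrolment time as a further source of unequal windows.

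A reader might infer that the plan must make a less effective dose look less safe. The documents do not support that. Death and early stopping shorten the window in poor responders, the longest optional windows need perceived benefit, flare re-treatment lengthens the window of earlier complete responders, and toxicity stops could make a more toxic dose look safer.

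**Conclusion.** The point holds as one of confounding with uncertain direction. That windows differ up to 2.6-fold, and depend on outcome, follows from the documents alone. The size of any gap does not. The 4 to 7 points at 10% risk per 28 days rest on an assumed constant hazard, an assumed 60% versus 30% CR split, optional treatment taken in full and no early stops. Across the simulated settings the gap runs from +5.3 to −3.5 points. A lower-CR dose tends to look less safe only if deaths and early stops among subjects without CR are few and event risk does not fall steeply over time. Because the sign is unknown, a reader cannot correct for it by eye. The consequence is for interpretation of the primary safety tables, not for any test.

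**What to change.** In SAP 4.3.8.1.2, 4.3.8.2 and 4.3.8.3, keep the existing tables and add two by dose group:

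1. **Fixed-window incidence** from first dose to a day that does not depend on response: Day 77 (last main-treatment dose plus 28 days), or Day 91 to match the infections table. State the day convention, since SAP 4.1.1 starts at analysis day 1 (visit Day 77 is analysis day 77 + 1 = 78).
2. **Exposure-adjusted incidence rates:** subjects with a first event divided by subject-time in the TEAE window, with time censored at first event, death, withdrawal or data cut-off.

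Add a sentence that any descriptive between-dose statement is read alongside these tables and not from the crude percentages alone.

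The cost is SAP wording and a few tables. Adverse events are collected from consent to end of trial (Protocol 6), and both fixed windows are complete at the Primary Analysis except for death or withdrawal. The additions have limits. The fixed window omits later on-treatment events and counts off-drug time for early stoppers, and the rates assume a roughly constant hazard. They supplement the planned tables and do not replace them.

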Long-term survival rates in steroid refractory (SR) patients are poor and range between 5–30%.

Recently, ruxolitinib (RUX) was approved by the United States (US) Food and Drug Administration (FDA) for the treatment of SR-GVHD in 2019 based on the results of the REACH 1 trial. In this single arm trial, 54.9% (39 patients) had an overall response, including 26.8% (19 patients) with a complete response (CR); moreover, median duration of response was 345 days, and the overall survival estimate at 6 months was 51.0%. Despite this improvement in treatment options, there is still considerable unmet medical need in this population, as a significant number of patients either do not respond to RUX (30–40%) or lose the initial response over time.

Apaglutide is a potent glucagon-like peptide 2 (GLP-2) receptor agonist, specifically designed to have slower absorption, decreased clearance, increased resistance to

proteolysis, and increased plasma protein binding compared with the marketed GLP-2 analog, teduglutide. In addition, once weekly dosing with apaglutide, supported by pharmacokinetic (PK) data from previous trials, could substantially reduce the burden of therapy, improve subject compliance and adherence, and reduce adverse reactions associated with subcutaneous (SC) administration compared with teduglutide daily dosing.

When administered subcutaneously to healthy animals, apaglutide exhibited a trophic effect resulting in the increase of the weight of the small intestine (80–180% increase in Sprague-Dawley rats and 20–80% increase in minipigs across different dose levels and time points), and, to a lesser extent the large intestine as well [Apaglutide Investigator Brochure]. In animal models of chemotherapy-induced intestinal mucosal injury, where the intestinal mucosa was severely injured by cytotoxic agents such as cytarabine or melphalan, apaglutide promoted mucosal healing and preserved the physical integrity and barrier function of the small intestine. Clinically, such pharmacological activity translates to the animals in attenuation of the body weight loss and in reduced mortality (40% of the apaglutide treated mice survived after Day 9 compared with no mice in the vehicle treated group; $p=0.0134$) without interfering with the anticancer efficacy of the chemotherapy, or with the efficacy of stem cell transplantation [Apaglutide Investigator Brochure].

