## 4 STATISTICAL METHODOLOGY

### 4.1 General Considerations

Unless otherwise specified, continuous data will be summarized descriptively by apraglutide dose group (High Dose, Low Dose, Total Randomized, Low Body Weight, Total) and by time point. Descriptive statistics for continuous variables will include: the number of subjects, mean, standard deviation (sd), median, first and third quartiles (Q1, Q3), minimum, and maximum. All raw data will be presented to the original number of decimal places. Where appropriate, mean, median, and confidence interval will be presented to one more decimal, while standard deviation will be reported to two more decimals.

Unless otherwise specified, categorical data will be summarized descriptively by apraglutide dose group (High Dose, Low Dose, Total Randomized, Low Body Weight, Total) and time point. Summary statistics for categorical variables will contain counts and percentages. The numbers and percentages of missing data for a variable will be reported when applicable. Percentages will be reported to one decimal except for zero and one hundred percent, which will be presented as 0% and 100%, respectively; unless otherwise specified, the percentages are based on the number of subjects in the respective analysis set. Two-sided 95% confidence intervals for single proportion will be estimated via Clopper-Pearson exact method.

Analyses will be performed using SAS® (version 9.4 or higher, SAS Institute Inc., Cary NC.) and/or R (version 4.1.0 or higher, R Foundation for Statistical Computing, Vienna, Austria). When possible, note that the preferred use of methods: Hyndman and Fan's Definition 2 (1996) for quantiles estimation, "half away from zero" for rounding.

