#### 4.2.3 *Safety Analysis Set 1*

Safety Analysis Set (SAS1) comprises all the randomized subjects exposed to at least one dose of apaglutide. All safety analyses will be carried out on the SAS1 according to the actual dose of apaglutide received. All principal safety analyses of subjects randomized on low or high doses of apaglutide will be carried out on the SAS1. Subjects will be analyzed according to the dose level of apaglutide received.

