#### 4.2.4 *Safety Analysis Set 2*

Safety Analysis Set (SAS2) comprises all the subjects included in FAS and exposed to at least one dose of apaglutide. All safety analyses will be carried out on the SAS2 according to the actual dose of apaglutide received (if a subject receives both dose levels during the course of the trial, this subject will be assigned to the High Dose group). Supportive safety analyses will be carried out on the SAS2.

When analyses are displayed in a single layout for both SAS1 and SAS2 (using a 5-column format), this document will refer to analysis on “SAS”.

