#### *4.3.8.1.3 Post-treatment Adverse Events Analysis*

The following type of events will be summarized by SOC and PT:

- 1) Adverse Events
- 2) Serious Adverse Events (SAE)
- 3) Grade 3-5 AE
- 4) Grade 5 AE
- 5) AE leading to study discontinuation
- 6) Related AE
- 7) Related Grade 3-5 AE
- 8) Related Grade 5 AE

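### Post-treatment AE percentages are taken over all treated subjects, including those who never reached the post-treatment period

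*SAP*

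**What the plan says.** SAP 4.3.8.1 splits follow-up into mutually exclusive pre-treatment, on-treatment and post-treatment periods. Events count as treatment-emergent until 28 days after the last dose, and then: "A post-treatment adverse event is defined as an AE occurring 28 days after the last dose". SAP 4.3.8.1.3 introduces eight kinds of post-treatment event with "The following type of events will be summarized by SOC and PT". They include serious, Grade 3-5, Grade 5 and related events. The section names no denominator, number at risk or observation time.

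The denominator therefore comes from two general rules. SAP 4.3.8: "Safety analysis will be performed by Dose levels (Low Dose, High Dose, Total Randomized, Low Body Weight, Total), on the SAS". SAP 4.1: "unless otherwise specified, the percentages are based on the number of subjects in the respective analysis set". The safety sets require exposure only. SAS1 (SAP 4.2.3) "comprises all the randomized subjects exposed to at least one dose", and SAS2 (SAP 4.2.4) "comprises all the subjects included in FAS and exposed to at least one dose". Neither has a condition on follow-up after the last dose.

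Three timing facts matter:
- Dosing runs to Week 7. It continues to Week 12 without a complete lower GI response at Week 8, and optional or flare dosing can reach Week 25 (SAP 2.1).
- The Primary Analysis uses data up to 01 Dec 2023, when every subject has reached Day 91 or withdrawn (SAP 1).
- Unless stated otherwise, analyses are run at both the Primary and the EOT step (SAP 1).

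**The concern.** A subject can contribute a post-treatment AE only if alive and under AE collection more than 28 days after the last dose and before the data cut. Two groups fail that condition: subjects who die on treatment or within the 28-day window and, at the Primary Analysis, subjects still dosing or too recently off treatment. Under the stated rules both stay in the denominator as if they had been watched and found event-free.

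Safety and tolerability is the primary objective (Protocol 1.5.1.1). A reader who takes the post-treatment percentages as the risk after stopping apraglutide would read them too low. Later dosing is also tied to lack of complete response, so the subjects missing from the period are not a random subset.

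The SAP already applies the matching principle to efficacy: in SAP 4.3.9, visits that are censored or not expected leave the response denominator. It has no equivalent rule for AEs.

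**Working it through.** The plan states no post-treatment incidence and no number entering that period, so there is no figure to reproduce. The check is timeline arithmetic plus a ratio.

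**1. When the period opens.** Opening day = last-dose day + 28, using nominal visit days.

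| Last dose | Last-dose day | Period opens after | Post-treatment days by Day 91 | No post-treatment time at 01 Dec 2023 if first dosed on or after |
|---|---|---|---|---|
| Week 7 | 49 | Day 77 | 14 | 15 Sep 2023 |
| Week 12 | 84 | Day 112 | 0 | 11 Aug 2023 |
| Week 25 | 175 | Day 203 | 0 | 12 May 2023 |

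The last column is 01 Dec 2023 minus 77, 112 and 203 days. A subject who has not withdrawn must have reached Day 91 by the cut-off, so was first dosed by 01 Sep 2023 (01 Dec minus 91 days). The consequences are:
- Every 8-dose completer still in follow-up has at least about 14 post-treatment days.
- A 13-dose completer has none only if first dosed between about 11 Aug and 01 Sep 2023, roughly three weeks of enrolment.
- A subject dosed to Week 25 has none if first dosed on or after about 12 May 2023.

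**2. Effect on the percentage.** Let x be subjects with a post-treatment event, N the safety-set number in the column, and m the number observed beyond last dose + 28 days. Printed = x/N and at-risk = x/m, so printed = at-risk × (m/N). The two agree only when m = N.

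**3. Size.** The documents do not give m, so this is a range under an assumed x = 3:

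| N | Printed x/N | At-risk x/m |
|---|---|---|
| 15 (one randomized arm) | 3/15 = 20.0% | m = 12: 25.0%; m = 9: 33.3% |
| 34 (all planned subjects) | 3/34 = 8.8% | m = 27: 11.1%; m = 20: 15.0% |

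**4. Deaths inside the 28-day window.** Protocol 1.1 cites a single-arm ruxolitinib trial in which "the overall survival estimate at 6 months was 51.0" per cent. Assuming a constant hazard, λ = −ln(0.51)/182.5 = 0.00369 per day. Of those alive at any last dose, 1 − exp(−0.00369 × 28) = 9.8% die within the next 28 days. If six-month survival were 70% (an assumption), the figure is 5.3%. Deaths before the planned end of dosing are additional, but their number depends on the unknown mix of course lengths and early stops.

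**5. Withdrawals.** AEs are collected for 4 weeks after early trial discontinuation (Protocol 6). A subject who leaves d days after the last dose is covered to day d + 28, which gives d days of post-treatment time. That is zero for someone leaving on the last-dose day and 14 days for someone leaving two weeks later. It is less if consent to further data is withdrawn. Stopping treatment alone does not end follow-up (Protocol 2.2.6).

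**The case against.** The strongest reply is that x/N is a legitimate quantity: the proportion of all treated subjects with an observed post-treatment event, with counts printed beside it. The at-risk denominator conditions on surviving and staying on trial, so dose groups compared on m are selected survivors. A rule of any observed time also weights one day the same as many months. This stands. It argues for showing both denominators and a time-based rate, not for leaving m unreported.

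Second, the still-dosing component is narrow (step 1) and is gone by the EOT analysis, which follows subjects for up to two years. That stands too. Deaths on treatment or within the window still affect both analyses.

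Third, the default in SAP 4.1 yields to other specifications, and table programming sits in a separate document (SAP 5). That document might set another N, but the SAP as written does not.

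Two stronger readings are tempting, and the documents support neither.
- A reader might apply the cited 51.0% survival from Day 0 and infer shortfalls of 25%, 34% and 53% for 8-, 13- and 26-dose courses (14%, 20% and 33% at 70% survival). That applies mortality from Day 0 to subjects defined by having completed the course. Anyone given the Week 25 dose was alive at Day 175, so only the next 28 days can remove them: about 10%, or 5% at 70% survival.
- A reader might infer that the dose comparison is tilted toward the worse arm. Deaths on treatment or within 28 days appear as Grade 5 treatment-emergent events by dose (SAP 4.3.8.1.2). Disposition and treatment duration are also shown by dose (SAP 4.3.1, 4.3.6.1), and no formal dose comparison is planned (SAP 6, item 12).

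**Conclusion.** The point holds as a reporting defect in the post-treatment AE tables. By the SAP's stated rules, subjects who never enter the period are counted as event-free in it, so the percentages are diluted by m/N as a measure of risk after treatment. The size is unknown because m is not given; the 20.0% against 25.0% or 33.3% example rests on assumed values of x and m. Part of the dilution at the Primary Analysis follows from the dosing schedule and cut-off, and resolves by the EOT analysis. The part due to deaths on treatment or within 28 days of the last dose remains. Withdrawals contribute less than one might expect, because AE collection continues for four weeks. The treatment-emergent tables are not affected.

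**What to change.** In SAP 4.3.8.1.3:
- Define the post-treatment at-risk number as SAS subjects alive and under AE collection beyond last dose + 28 days and before the cut-off. Print it per column beside the SAS N.
- Use it as the denominator for post-treatment percentages.
- Add subjects with an event per unit of post-treatment observation time (for example per 100 subject-weeks), because follow-up in this period varies widely.
- Note that the at-risk number conditions on surviving and remaining on trial, and refer the reader to the Grade 5 treatment-emergent table.

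Apply this at both the Primary and the EOT analysis. The cost is a short SAP paragraph, one derived flag and one derived duration from dates already collected. No new data are needed. The downside is the selection in the at-risk group, which showing both denominators keeps visible.
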